use in child psychiatry is novel. Creatine's gender-specific effects in animal models mandate that studies in youth be initially limited to female participants. Expanding upon our group's recent completion of a multidose study to establish which of four daily creatine doses offers the best combination of efficacy, safety and tolerability in adolescent females with SSRI-resistant MDD, we propose to conduct a pilot, placebo-controlled study of 10g daily adjunctive creatine, the dose selected from the dose-ranging trial, for adolescent females with SSRI-resistant MDD. We propose to examine the relationship between depression severity and cerebral PCr and to measure the effect size of adjunctive creatine vs. placebo on brain chemistry and clinical outcome in adolescent females with SSRI-resistant MDD.

OBJECTIVES:

The primary hypothesis is that compared to placebo, 10g of daily creatine monohydrate for eight weeks will be associated with significant increases in frontal lobe PCr and β -NTP concentrations. A secondary hypothesis is that decreased depressive symptoms measured with the CDRS-R and Montgomery Asberg Depression Rating Scale (MADRS) will be reciprocally correlated with increased β -NTP concentrations.

PARTICIPANT SELECTION CRITERIA:

Thirty-three female adolescents with MDD will be randomly assigned in a 1:1 ratio to either treatment for eight weeks, for a total of 66 MDD participants. Additionally, 40 healthy adolescents will be recruited as comparison subjects for the study. Key inclusion, exclusion, and study withdrawal criteria for each subject group are summarized below.

MDD SUBJECTS

Inclusion Criteria:

- Participants must be female.
- Participants must be able to grant informed consent (age ≥ 18), or parent/guardian permission plus participant assent (age < 18).
- Participants must meet DSM-IV criteria for MDD, with current mood state depressed for > 2 weeks.
- Participants must be between the ages of 12 and 21.
- Current CDRS-R raw score of ≥ 40 or MADRS score ≥ 25 ; and CGI-S score ≥ 4 .
- Participants may be enrolled in individual and/or group psychotherapy, if it has been ongoing for at least 8 weeks.

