We hypothesize that at baseline, CDRS-R scores are negatively correlated with cerebral PCr in female adolescents with SSRI-resistant MDD. We also hypothesize that for participants whose MDD responds to creatine, change CDRS-R score will be inversely correlated with change in brain beta-NTP levels (i.e. participants who have a significant decrease in their CDRS-R score will show an increase in beta-NTP).

Both intent-to-treat (ITT; encompasses all participants who receive >1 dose of study drug) and protocol completer analyses will be performed. A participant completing 8 weeks of treatment and both ^{31}P -MRS scans will be considered a "completer." Data will be expressed as mean + standard deviation (SD). Group differences in demographic variables involving continuous data will be calculated using one-way analysis of variance. Between-group comparisons involving categorical variables will be assessed using Fisher's exact test for n x k contingency tables. A linear mixed model (LMM) will be used to account for the association between measurements (baseline and post-treatment) for each individual for the repeated measures analysis. Exploratory data analysis using non-parametric statistical tests (e.g., Wilcoxon Rank-Sum test and the Mann-Whitney U-test) will also be performed. Statistical significance will be defined at the two-tailed, 0.05 level. Stata 11 (StataCorp LP, College Station, TX) and SAS 9.2 (SAS Institute, Cary, NC) software will be used for statistical calculations. Confidence intervals for all estimated parameters will be constructed using a 95% level.

Power Analysis and Sample Size Calculations: Calculations are based on the open-label female adolescent SSRI-resistant MDD creatine data obtained at our site, and our adult creatine studies. All power calculations are two-tailed with an alpha level of 0.05, and were performed in the specialized software PASS (NCSS, Kaysville, UT). The minimum required sample size

satisfying our hypothesis is 30 creatine-treated, 30 placebo-treated, and 30 age-matched healthy controls. Assuming a 10% attrition rate for MDD subjects and a 30% attrition rate for healthy controls, we propose to enroll a total of 66 female adolescents with SSRI-resistant MDD and 40 healthy controls. The central hypothesis and power analysis for the R33 clinical trial are described below.

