The hypothesis that PCr and beta-NTP levels measured with 31P-MRS will show significant change associated with 8 weeks of 10g daily creatine compared with placebo in female adolescents with SSRI-resistant MDD evaluates the significance of treatment-related recovery. In our open-label creatine data, we found that female adolescents with SSRI-resistant MDD showed increased PCr and decreased beta-NTP following creatine augmentation. The effect size of these changes were estimated to be approximately 1.0 (Cohen's d) with 10% SD. Therefore, when we conservatively set the effect size to be 0.9; sample size of 30 per each group; and common SD within a group of 10%, the changes of metabolite levels between creatine and placebo groups will be significantly (alpha level of 0.05) detectable with 86% of power.

ADMINISTRATIVE RESPONSIBILITIES

Resources:

The Brain Institute

The facilities at the University of Utah that are available for the proposed research include the following: the Brain Institute and UNI. The Brain Institute currently occupies 5,900 square feet of office and laboratory space in a building in the University of Utah Research Park adjacent to the Health Sciences campus. It also occupies clinical space in UNI, the site of the Brain Institute's Siemens 3T MRI research scanner.

Recruitment of Participants:

- No “cold calls” will be made by members of the study team.
- An informational flyer will be placed (with permission) on public bulletin boards. The flyer will be submitted to the IRB for approval prior to posting. Examples of public bulletin boards may include but are not limited to: University of Utah bulletin boards (for example, the Health Science Education Building, the College of Nursing, the Department of Psychology, etc.), the Salt Lake Community College, and business frequented by adolescents and their parents.
- An informational brochure has been created, to be displayed (with permission) in appropriate public areas, and to be provided to practicing mental health clinicians, pediatricians and family practitioners in the Salt Lake City area. The clinicians, at their sole discretion and without compensation, will pass the brochure to the parent(s) or guardian(s) of adolescent clients in cases where they deem it appropriate. The brochure will be submitted to the IRB for approval, prior to distribution to clinicians.

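### The only beta-NTP effect size behind the power claim is attached to a fall, but the primary hypothesis predicts a rise; and the stated inputs give about 93% power, not 86%

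*Combined protocol and SAP*

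**What the plan says.** The Objectives section holds the only statement labelled the primary hypothesis: over eight weeks, 10 g of creatine daily "will be associated with significant increases in frontal lobe PCr and" beta-NTP, relative to placebo. The secondary hypothesis there links falling depression scores to rising beta-NTP. Statistical Analyses repeats the link for creatine responders: "participants who have a significant decrease in their CDRS-R score will show an increase in beta-NTP".

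Power Analysis and Sample Size Calculations names its source: "Calculations are based on the open-label female adolescent SSRI-resistant MDD creatine data obtained at our site, and our adult creatine studies". It then announces: "The central hypothesis and power analysis for the R33 clinical trial are described below". The hypothesis that follows is that PCr and beta-NTP "will show significant change associated with 8 weeks of 10g daily creatine compared with placebo". The next sentence reports that open-label participants "showed increased PCr and decreased beta-NTP following creatine augmentation". On size, it says: "The effect size of these changes were estimated to be approximately 1.0", with an SD of 10%. The effect size is then lowered to 0.9 as a conservative step. With 30 per group and a common SD of 10%, the difference between arms is said to be "detectable with 86% of power". All power calculations are two-tailed at 0.05.

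Three background statements bear on direction:
- The section on metabolic changes in depression gives reduced beta-NTP with increased PCr as the adult MDD pattern, and says creatine can produce equivalent changes in healthy adults.
- The Creatine Supplementation section describes the same healthy-volunteer study and reports only a rise in PCr.
- The section on creatine's antidepressant effects in females says that, in the dose-ranging study, only the 10 g group showed a rise in frontal beta-NTP.

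**The concern.** The power figure is offered for both metabolites. For PCr, the hypothesis and the open-label data agree on a rise. For beta-NTP, the hypothesis predicts a rise, while the data used to size the trial are said to show a fall. An effect size taken from a fall is not evidence that a rise of that size is plausible.

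If the reported fall is correct and carries over to this trial, the beta-NTP half of the primary hypothesis has almost no chance of being confirmed. If it is a drafting slip, the plan misreports its own planning data. In either case the stated power cannot be relied on for that half.

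The 86% also does not follow from the inputs beside it, so a reader cannot tell what was calculated.

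**Working it through.** **Inputs.** From the power paragraph: d = 0.9, SD 10%, 30 per arm, power 86%. From the sample-size text: two-sided alpha 0.05. I take a two-sample t-test on change, with df = 58.

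**1. The plan's own figure.** The noncentrality parameter is d × √(n/2) = 0.9 × √15 = 3.486.
- Noncentral t, two-sided 0.05: 92.9%.
- Normal approximation: 93.6%.
- One-sided 0.05: 96.4%.
- Two-sided 0.025, as if alpha were split over two metabolites: 87.9%.

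The first two use the stated inputs, and neither gives 86%.

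**2. What would give 86%.** The plan states none of these inputs:

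| Unstated input | Power |
|---|---|
| d = 0.80, 30 per arm | 86.1% |
| d = 0.9, 24 per arm | 86.3% |
| Both metabolites significant, if independent: 0.929² | 86.3% |
| 10% is the SD of levels, baseline-to-week-8 correlation ρ = 0.37 | 86.3% |

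For the last row, the effect size on change is 0.9/√(2(1 − ρ)) = 0.9/√1.26 = 0.80. At ρ = 0.5 the divisor is 1 and the power returns to 92.9%.

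**3. Sign and two-sided power.** Power is 92.9% at d = +0.9 and 92.9% at d = −0.9. The figure is the same for either direction, so it cannot show which one the planning data support.

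**4. Chance of the result that the Objectives predict for beta-NTP.** This is the probability of a significant increase with 30 per arm at two-sided 0.05:

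| True d | Probability |
|---|---|
| −0.9 (open-label direction, planning size) | about 0.000004% |
| 0 | 2.5% |
| +0.3 | 21% |
| +0.5 | 48% |
| +0.7 | 76% |
| +0.9 | 93% |

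The values of d other than ±0.9 are my illustrations. At an SD of 10%, d = 0.9 is 0.9 × 10% = 9% between arms. The document gives no size for any beta-NTP increase to compare with this.

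**5. The statements on beta-NTP side by side.**

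| Place | Direction | Size |
|---|---|---|
| Objectives, primary hypothesis | rise | none |
| Statistical Analyses, responders | rise | none |
| Power paragraph, open-label data | fall | about 1.0, set to 0.9 |
| Dose-ranging study, 10 g | rise | no magnitude, SD or arm size |
| Healthy adults, equivalent changes | fall, if read literally | none |
| Same healthy-adult study, second account | PCr rise only | none |

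The adult studies named as a second planning source come with no figure. The open-label dose is not stated, so a dose explanation for the two directions cannot be checked.

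**The case against.** Several objections have force.

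*Sign does not matter for two-sided power.* This is correct. It would be wrong to infer that the calculation is invalid because of the sign. What lacks support is using 0.9 as the size of a beta-NTP increase.

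*The hypothesis is not really stated in two ways.* A reader might infer that two rival hypotheses are in force and that a rise and a fall could each be claimed as confirmation. The document does not support that. Only the Objectives statement is labelled primary, and it is directional. Speaking of change is ordinary in a two-tailed power paragraph, and the clinical hypotheses also tie improvement to rising beta-NTP. A significant fall would contradict the primary hypothesis. Aligning the wording is still worthwhile, because the power paragraph calls its version central and follows it with a fall.

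*The reported fall is probably a slip.* This is plausible. It is the only explicit statement that creatine lowered beta-NTP, and the account of the open-label study in the background mentions only a PCr rise. But the healthy-adult comparison can be read as agreeing with a fall. The document cannot settle it, and it would be equally wrong to infer that the open-label data refute the hypothesis.

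*The dose-ranging study justifies the direction.* It may explain why the Objectives predict a rise. It gives no size, and the sample-size text does not name it as a source.

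*86% may be right if 10% is the SD of levels.* This needs a correlation that the plan does not give, and it sits poorly with a paragraph that attaches the effect size to the changes themselves. It supports stating the missing input, not leaving the figure as it is.

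*It is a pilot, and two-sided tests with 95% confidence intervals will show the sign.* Both are true, and both limit the consequence.

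**Conclusion.** The point holds for beta-NTP only. The single effect size offered for it belongs to a fall, the primary hypothesis predicts a rise, and nothing in the document gives the size of a rise. The power claim for that half of the hypothesis is therefore unsupported. The PCr half has no sign conflict.

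The stated 86% is a separate error of reporting. The stated inputs give 92.9% per metabolite, assuming a two-sample t-test on change with 10% as the SD of change. A reader might infer that the trial is too small. That does not follow: on the stated inputs, the power per metabolite is understated.

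Confidence is high on the mismatch and on the missing size for a beta-NTP increase. Whether the reported fall is a slip is unknown. The consequence is for how the beta-NTP result is justified and read, not for whether a difference can be detected. It should be fixed before unblinding.

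**What to change.** 1. Check the reported beta-NTP fall against the open-label data. Reconcile it with the Objectives, the responder hypothesis, the healthy-adult comparison and the dose-ranging result.
2. Before unblinding, make the hypothesis in the power paragraph match the direction in the Objectives for each metabolite. Keep the two-sided test. Add that a significant beta-NTP effect in the opposite direction will be reported as contrary to the primary hypothesis.
3. If the fall is a slip, correct it and give the signed open-label effect size. If it is correct, stop using it to support power for an increase. Then either base beta-NTP power on a signed effect size, with its 95% CI, from the 10 g and placebo arms of the dose-ranging study, or state power for PCr only.
4. In either case, restate the power as about 93% per metabolite from the stated inputs, or give the input that yields 86%.

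The cost is one data check, matched wording in two places and one recalculation. Sample size, endpoints and test do not change. The downside is that the beta-NTP power statement may be dropped or become less favourable.

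### The stated 86% power does not follow from the stated inputs, which give 93%, and 40 controls with 30% attrition leave 28, not the required 30

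*Combined protocol and SAP*

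**What the plan says.** Under *Power Analysis and Sample Size Calculations* (within *Statistical Analyses*), the plan sets general conditions: "All power calculations are two-tailed with an alpha level of 0.05, and were performed in the specialized software PASS". The minimum number "satisfying our hypothesis is 30 creatine-treated, 30 placebo-treated, and 30 age-matched healthy controls". Attrition is taken as 10% for participants with MDD, and with a "30% attrition rate for healthy controls, we propose to enroll a total of 66 female adolescents with SSRI-resistant MDD and 40 healthy controls".

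The calculation for the creatine versus placebo comparison follows. The open-label data are said to show an effect of about 1.0 (Cohen's d) with a 10% SD. Then, "when we conservatively set the effect size to be 0.9; sample size of 30 per each group; and common SD within a group of 10" per cent, "the changes of metabolite levels between creatine and placebo groups will be significantly (alpha level of 0.05) detectable with 86% of power".

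No test or PASS procedure is named for this calculation. The analysis text says only that "A linear mixed model (LMM) will be used to account for the association between measurements (baseline and post-treatment) for each individual". The primary hypothesis under *Objectives* covers two metabolites: creatine "will be associated with significant increases in frontal lobe PCr and" β-NTP concentrations. The plan states no joint success rule, multiplicity adjustment or pre-post correlation.

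**The concern.** Effect size, group size, level and sidedness are all given, so the power of a simple two-group comparison is fixed. For d = 0.9 and 30 per group, 86% looks too low. The control numbers look inconsistent within adjacent sentences: losing 30% of 40 leaves fewer than 30.

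This is the only numerical support for randomising 66 participants. If 86% came from a smaller effect size or from requiring both metabolites to succeed, a reader would need to know. The second case would also imply a decision rule that the analysis section does not contain. The trial is meant to inform a later efficacy study, so its sample-size basis should be traceable.

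**Working it through.** **Inputs.** From *Power Analysis and Sample Size Calculations*: d = 0.9, SD = 10%, n = 30 per group, two-tailed alpha = 0.05, attrition of 10% (MDD) and 30% (controls), enrolment of 66 MDD and 40 controls. Allocation is 1:1 (*Design*).

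**Attempt to reproduce 86%.** The SD cancels: a difference of 0.9 × 10% = 9 percentage points, divided by an SD of 10%, is 0.9 again. For a two-sample t-test:

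- degrees of freedom = 30 + 30 − 2 = 58
- non-centrality = d × √(n/2) = 0.9 × √15 = 3.486
- power from the non-central t, two-sided 0.05 = **92.9%**

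The normal approximation gives 93.6%. With 29 per arm the t-test gives 92.0%. The stated 86% is not reproduced, and a gap of about seven points is not rounding.

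**Smallest n for 86% at d = 0.9.** 24 per arm gives 86.3% and 23 gives 84.7%.

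**Other readings, 30 per arm.**

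| Reading | Power | Stated in the plan? |
|---|---|---|
| t-test, d = 0.8 | 86.1% | No; 0.9 is stated |
| Both metabolites significant, independent, d = 0.9 | 0.929² = 86.3% | No joint rule or independence stated |
| Change score, 10% as SD at one time point, correlation 0.36 | about 86% | No correlation given |
| Alpha 0.025 per metabolite, d = 0.9 | 87.9% | No; 0.05 is stated |
| Mann-Whitney, d = 0.9, normal data | 91–92% | Exploratory only |

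For the change-score row, the effective effect is 0.9/√(2(1 − ρ)). The correlation ρ is an assumption, and the result depends strongly on it:

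| ρ | 0.3 | 0.4 | 0.5 | 0.7 |
|---|---|---|---|---|
| Power | 82.6% | 87.9% | 92.9% | 99.3% |

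**Power at the expected numbers.** Retention is 33 × 0.9 = 29.7 per arm. With 29 per arm, power is 92.0% on the written inputs, 84.9% if d = 0.8 was meant, and 0.920² = 84.7% for joint success under independence.

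**Healthy controls.**

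- Retained: 40 × (1 − 0.30) = **28**, against a stated minimum of 30
- Needed to retain 30: 30/0.70 = 42.9, so 43
- Attrition at which 40 leaves 30: 1 − 30/40 = 25%

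Multiplying instead of dividing gives 30 × 1.3 = 39, close to the planned 40. That may explain the figure, but it is a conjecture.

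**MDD participants.** 66 × 0.9 = 59.4, or 29.7 per arm against 30. 60/0.9 = 66.7 would round up to 67. The shortfall is a fraction of a participant.

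**The case against.** The plan never says that a t-test was used. PASS offers other procedures, the analysis is a mixed model, and the hypothesis names two metabolites, so 86% may be a correct result for a calculation the sentence describes incompletely. That is possible, and the documents cannot rule it out. But each such reading needs an input that is absent from the text. The sentence is then incomplete rather than miscalculated, and it needs correction either way.

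The plan also does not tie its minimum of 30 to 86% power or to d = 0.9. This is fair. The remark that 24 per arm would suffice applies only if this calculation, the only one shown, is the basis of that minimum.

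The multiplicative slip suggested for the controls gives 39 rather than 40, while the same rule gives exactly 66 for MDD (60 × 1.1). The cause therefore remains open. The mismatch of 28 against 30 does not depend on it.

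Printing 93% could suggest more confidence than the data warrant. The 0.9 is derived from open-label changes, not from a contrast with placebo, and the plan reports that β-NTP fell in those data while *Objectives* predicts a rise. This stands as a caution: 93% is what the written inputs imply, not an endorsement of those inputs.

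Finally, this is a pilot, and no recruitment decision changes. That bears on the importance of the point, not on its correctness.

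**Conclusion.** Both figures are wrong as written. On the stated inputs, and taking the comparison as a two-sample t-test, power is 92.9% rather than 86%. The source of the 86% cannot be recovered from the documents. The enrolment of 40 controls yields 28 at the plan's own attrition rate, two short of its stated minimum.

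The practical impact is low. On the written inputs the error understates power, and the least favourable readings above lose only about one point from the stated 86% with 29 per arm. The randomised sample of 66 is not undermined by this error. The controls have no power calculation of their own and are not part of the randomised comparison, so their shortfall is a consistency error.

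**What to change.** Retrieve the PASS output and rewrite the power sentence so that procedure, effect size, sample size and power agree:

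- If the basis was a t-test with d = 0.9, state 93% power for each metabolite at 30 per arm and 92% at 29, with the open-label origin of the effect size made plain.
- If it was something else, state the effect size, the joint success criterion, or the SD and correlation that gave 86%, with the power at 29 to 30 evaluable per arm.

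Do not call 30 per arm the minimum unless it is the minimum for the power then stated.

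For the controls, replace the minimum of 30 with about 28 expected evaluable (40 enrolled, 30% attrition). Nothing shown in the plan depends on exactly 30. If the sponsor does need 30, the figures agree only with 43 enrolled or with a justified attrition of at most 25%.

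The recommended change costs wording and restated figures only. It adds no patients or controls.
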